### **6.3. Clinic Visit 2 (Week 1/Day 8 ±1 day)**

At this visit, the investigator will review dosing with the subject and/or child's parents/legally acceptable representative and may adjust the dose based on seizure response and tolerability.

The following activities will be performed at Visit 2:

- Review and record adverse events.
- Review and record all concomitant medications and non-drug treatments/procedures.
- Complete assessment of suicidal ideation and behavior (C-SSRS or CBCL) using appropriate version or test for subject's age. If CBCL is administered, scores must be obtained as soon as possible. If positive scores are obtained on the CBCL or CSSRS, a mental health risk assessment must be performed by a qualified mental health professional prior to randomization (please refer to [Section 7 - ASSESSMENTS](#)).
- Collect and review daily seizure and dosing diary and record number and type of seizure.
- Adjust the dose if needed based on seizure response and tolerability.
- Evaluate and record study medication compliance.
- Dispense study medication via tele-randomization system.
- For direct-enrolling subjects assigned liquid solution, verify accurate dose administration via syringe/bottles. Have subject and/or child's parents/legally

acceptable representative demonstrate dosing in office to verify continued comprehension of dosing instructions.

- Dispense seizure and dosing diary and review instructions for completion.

#### **6.4. Clinic Visit 3 (Month 1/Day 30 ±4 Days)**

The following activities will be performed at Visit 3:

- Review and record adverse events.
- Review and record all concomitant medications and non-drug treatments/procedures.
- Collect and review seizure and dosing diary and record number and type of seizure.
- Adjust the dose if needed based on seizure response and tolerability.
- Complete assessment of suicidal ideation and behavior (C-SSRS or CBCL) using appropriate versions or test for subject's age. If CBCL is administered, scores must be obtained as soon as possible. If positive scores are obtained on the CBCL or CSSRS, a mental health risk assessment must be performed by a qualified mental health professional prior to randomization (please refer to [Section 7 - ASSESSMENTS](#)).
- Evaluate and record study medication compliance.
- Dispense study medication via tele-randomization system.
- Dispense subject daily seizure and dosing diary.

#### **6.5. Clinic Visit 4 (Month 2/Day 60 ±4 Days)**

The following activities will be performed at Visit 4:

- Review and record adverse events.
- Review and record all concomitant medications and non-drug treatments/procedures.
- Collect and review seizure and dosing diary and record number and type of seizure.
- Adjust the dose if needed based on seizure response and tolerability.
- Complete assessment of suicidal ideation and behavior (C-SSRS or CBCL) using appropriate version or test for subject's age. If CBCL is administered, scores must be obtained as soon as possible. If positive scores are obtained on the CBCL or CSSRS, a mental health risk assessment must be performed by a qualified mental health professional prior to randomization (please refer to [Section 7 - ASSESSMENTS](#)).

- Collect and record vital signs.
- Evaluate and record study medication compliance.
- Dispense study medication via tele-randomization system.
- Dispense subject daily seizure and dosing diary.

#### **6.6. Telephone Contact (Month 3/Day 90 ±4 Days)**

The Investigator (or designee) will contact the parent/subject by telephone to ensure medication compliance and provide guidance for accurate dosing as required.

- Review subject's compliance with dosing regimen.
- Review compliance with completion of dosing and seizure diary.
- Review concomitant medications and non-drug treatments/procedures.
- Assess adverse events.

#### **6.7. Clinic Visit 5 (Month 4/Day 120 ±4 Days)**

The following activities will be performed at Visit 5:

- Review and record adverse events.
- Review and record all concomitant medications and non-drug treatments/procedures.
- Collect and review seizure and dosing diary and record number and type of seizure.
- Complete assessment of suicidal ideation and behavior (C-SSRS or CBCL) using appropriate version or test for subject's age. If CBCL is administered, scores must be obtained as soon as possible. If positive scores are obtained on the CBCL or CSSRS, a mental health risk assessment must be performed by a qualified mental health professional prior to randomization (please refer to [Section 7 - ASSESSMENTS](#)).
- Evaluate and record study medication compliance.
- Dispense study medication via tele-randomization system.
- Dispense subject daily seizure and dosing diary.

#### **6.8. Telephone Contact (Month 5/Day 150 ±4 Days)**

The Investigator (or designee) will contact the parent/subject by telephone to ensure medication compliance and provide guidance for accurate dosing as required.

- Review subject's compliance with dosing regimen.
- Review compliance with completion of dosing and seizure diary.
- Review concomitant medications and non-drug treatments/procedures.
- Assess adverse events.

#### **6.9. Clinic Visit 6 (Month 6/Day 180 ±4 Days)**

The following activities will be performed at Visit 6:

- Review and record adverse events.
- Review and record all concomitant medications and non-drug treatments/procedures.
- Evaluate and record study medication compliance.
- Collect and review seizure and dosing diary and record number and type of seizure.
- Adjust the dose if needed based on seizure response and tolerability.
- Complete brief physical and neurological exams to include height, weight, vital signs.
- Collect blood samples for hematology, biochemistry.
- Collect urine samples for urinalysis and a urine pregnancy test (for female subjects who are menarchal).
- Complete assessment of suicidal ideation and behavior (C-SSRS or CBCL) using appropriate version or test for subject's age. If CBCL is administered, scores must be obtained as soon as possible. If positive scores are obtained on the CBCL or CSSRS, a mental health risk assessment must be performed by a qualified mental health professional prior to randomization (please refer to [Section 7 - ASSESSMENTS](#)).
- Dispense study medication via tele-randomization system.
- Dispense subject daily seizure and dosing diary.

#### **6.10. Telephone Contact (Month 7/Day 210 ±4 Days)**

The Investigator (or designee) will contact the parent/subject by telephone to ensure medication compliance and provide guidance for accurate dosing as required.

- Review subject's compliance with dosing regimen.
- Review completion of dosing and seizure diary.

- Review concomitant medications and non-drug treatments/procedures.
- Assess adverse events.

#### **6.11. Telephone Contact (Month 8/Day 240 ±4 Days)**

The Investigator (or designee) will contact the parent/subject by telephone to ensure medication compliance and provide guidance for accurate dosing as required.

- Review subject's compliance with dosing regimen.
- Review completion of dosing and seizure diary.
- Review concomitant medications and non-drug treatments/procedures.
- Assess adverse events.

#### **6.12. Clinic Visit 7 (Month 9/Day 270 ± 4 Days)**

The following activities will be performed at Visit 7:

- Review and record adverse events.
- Review and record all concomitant medications and non-drug treatments/procedures.
- Collect and review seizure and dosing diary and record number and type of seizure.
- Adjust the dose if needed based on seizure response and tolerability.
- Complete assessment of suicidal ideation and behavior (C-SSRS or CBCL) using appropriate version or test for subject's age. If CBCL is administered, scores must be obtained as soon as possible. If positive scores are obtained on the CBCL or CSSRS, a mental health risk assessment must be performed by a qualified mental health professional prior to randomization (please refer to [Section 7 - ASSESSMENTS](#)).
- Evaluate and record study medication compliance.
- Collect urine samples for a urine pregnancy test (for female subjects who are menarchal).
- Collect and record vital signs.
- Dispense study medication via tele-randomization system.
- Dispense subject daily seizure and dosing diary.

### **6.13. Telephone Contact (Month 10/Day 300 ±4 Days)**

The Investigator (or designee) will contact the parent/subject by telephone to ensure medication compliance and provide guidance for accurate dosing as required:

- Review subject's compliance with dosing regimen.
- Review completion of dosing and seizure diary.
- Review concomitant medications and non-drug treatments/procedures.
- Assess adverse events.

### **6.14. Telephone Contact (Month 11/Day 330 ±4 Days)**

The Investigator (or designee) will contact the parent/subject by telephone to ensure medication compliance and provide guidance for accurate dosing as required:

- Review subject's compliance with dosing regimen.
- Review completion of dosing and seizure diary.
- Review concomitant medications and non-drug treatments/procedures.
- Assess adverse events.

### **6.15. Clinic Visit 8 (Month 12/Early Termination Day 365 ±7 Days)**

The 12 month treatment phase is completed. Subjects who will not continue treatment with pregabalin, whether they complete, or require early termination prior to the completion of 12 months of treatment, should begin the taper as described in [Section 3 \(Table 1\)](#) and follow the procedures for Visits 8 and 9. Subjects who continue on pregabalin following completion of the study will not require a taper.

The following activities will be performed at Visit 8:

- Review and record adverse events.
- Review and record all concomitant medications and non-drug treatments/procedures.
- Collect and review seizure and dosing diary and record number and type of seizure.
- Perform 12-lead electrocardiogram (ECG).
- Complete brief physical examination to include height, weight, vital signs and assessment of Tanner stage (pediatric subjects only, but not applicable to subjects who participated to study A0081042).

- Complete full neurological examination.
- Complete assessment of suicidal ideation and behavior (C-SSRS or CBCL) using appropriate version or test for subject's age. If CBCL is administered, scores must be obtained as soon as possible. If positive scores are obtained on the CBCL or CSSRS, a mental health risk assessment must be performed by a qualified mental health professional prior to randomization (please refer to [Section 7 - ASSESSMENTS](#)).
- Administer CogState battery (POS pediatric subjects 4-16 years of age).
- Collect blood samples for hematology, biochemistry.
- Collect urine sample for urinalysis and a urine pregnancy test (for female subjects who are menarchal).
- Evaluate and record study medication compliance.
- Dispense taper medication if required via tele-randomization system.
- Dispense subject daily seizure and dosing diary if subject will begin taper.

#### **6.16. Visit 9 (Follow-up/End of Taper Visit-7 days Post-Completion/Discontinuation±3 Days)**

This visit is not required for subjects that do not enter the taper phase.

The following activities will be performed at Visit 9:

- Review and record adverse events.
- Review and record all concomitant medications and non-drug treatments/procedures.
- Collect and review seizure and dosing diary and record number and type of seizure.
- Collect urine sample for a urine pregnancy test (for female subjects who are menarchal).
- Evaluate and record study medication compliance.
- Complete assessment of suicidal ideation and behavior (C-SSRS or CBCL) using appropriate versions or test for subject's age. If CBCL is administered, scores must be obtained as soon as possible. If positive scores are obtained on the CBCL or CSSRS, a mental health risk assessment must be performed by a qualified mental health professional prior to randomization (please refer to [Section 7 - ASSESSMENTS](#)).

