## SCHEDULE OF ACTIVITIES

The Schedule of Activities table provides an overview of the protocol visits and procedures. Refer to [STUDY PROCEDURES \(Section 6\)](#) and [ASSESSMENTS \(Section 7\)](#) for detailed information on each procedure and assessment required for compliance with the protocol.

Study Period	Screening/ Baseline		12 Month Treatment Phase												End of Treatment & Taper Phase	
	Clinic Visit Number	Visit 1A	Visit 1B	Visit 2	Visit 3	Visit 4	TC*	Visit 5	TC*	Visit 6	TC*	Visit 7	TC*	Visit 8	Visit 9	
Study Month	Prior Study Subjects	Direct Enroll	Month 1	Month 2	Month 3	Month 4	Month 5	Month 6	Month 7	Month 8	Month 9	Month 10	Month 11	Month 12/EOS/ Early Term g Begin Taper	End Taper/ Follow up	
Study Day	Day 1A a	Day 1B a	8 (±1)	30 (±4)	60 (±4)	90 (±4)	120 (±4)	150 (±4)	180 (±4)	210 (±4)	240 (±4)	270 (±4)	300 (±4)	330 (±4)	365 (±7)	7 days post completion i (±3)
Informed Consent/Assent	X	X														
Record Demographic Information	X	X														
Record Medical History	X b	X														
Record Seizure History	X b	X														
Perform Physical and Neurological Examination	X b	X d							X						X d	
Review Inclusion/Exclusion Criteria	X	X														
Record Antiepileptic Medication History	X b	X														
Record All Prior Medications	X b	X														
Record all concurrent medications and non-drug treatment/procedures (include any ongoing AEDs)	X	X	X	X	X	X	X	X	X	X	X	X	X	X	X	X

Study Period		Screening/ Baseline		12 Month Treatment Phase												End of Treatment & Taper Phase	
Clinic Visit Number		Visit 1A	Visit 1B	Visit 2	Visit 3	Visit 4	TC*	Visit 5	TC*	Visit 6	TC*	Visit 7	TC*	Visit 8	Visit 9		
Study Month		Prior Study Subjects	Direct Enroll	Month 1	Month 2	Month 3	Month 4	Month 5	Month 6	Month 7	Month 8	Month 9	Month 10	Month 11	Month 12/EOS/ Early Term g Begin Taper	End Taper/ Follow up	
Study Day	Day 1A a	Day 1B a		8 (±1)	30 (±4)	60 (±4)	90 (±4)	120 (±4)	150 (±4)	180 (±4)	210 (±4)	240 (±4)	270 (±4)	300 (±4)	330 (±4)	365 (±7)	7 days post completion i (±3)
Perform 12-Lead Electrocardiogram (ECG)	X b	X														X	
Collect and Record Vital Signs	X b	X			X					X			X			X	
Record Height & weight	X b	X								X						X	
Collect Urine Sample for Pregnancy Test c	X b	X								X			X			X	X

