b. If procedures were performed during participation in Studies A0081041, A0081042, or A0081105 the actual procedure will not need to be repeated for the Study A0081106 Screening Visit 1A (data from the subject's previous study will be utilized).

- For at-risk subjects, a mental health risk assessment must be performed by a qualified mental health professional.

c. Female subjects who are menarchal must have negative urine pregnancy test. Pregnancy tests may be completed more frequently as per IRB's/IEC's or as required based upon local regulations.

d. Include Tanner stage assessment at screening for direct enrolling pediatric/adolescent, and at last visit Month 12 for all pediatric/adolescent subjects only. This assessment is not applicable to subjects who participated in study A0081042.

- e. This is a taper medication dispensation only for subjects who will cease treatment with pregabalin. If the subject will continue to receive pregabalin treatment post-study, initiation of taper is at the discretion of the investigator. Subjects who require early discontinuation and require taper, should begin the taper at the time the decision is made to discontinue. These subjects should return approximately 1 week later for follow-up Visit 9.
- f. Assessment of suicidal ideation and behavior:
  - I. MINI-KID only for children and adolescents 6 -<17 years of age at Visit 1B or if they did not have a MINI-KID performed during prior participation to studies referred in Visit 1A.
  - II. C-SSRS "Lifetime" version performed at Visit 1 for all subjects aged 6-65 years who did not have a C-SSRS performed previously. C-SSRS "Since Last Visit" version for all subjects ages 6-65 years for each visit beginning at Visit 2 through Visit 9 or Early Termination.
  - III. Child Behavior Checklist (CBCL) performed for children 4-<6 years of age beginning at Visit 1 and at every subsequent visit until Visit 9 or Early Termination.

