- g. Month 12, Visit 8 is the End of Treatment/End of Study visit for subjects who will not initiate taper of pregabalin per the discretion of the investigator. Visit 8 will be the final study visit for these subjects. For subjects who will taper their pregabalin treatment, Visit 8 is considered End of Treatment/End of Study Visit but they will initiate taper at this visit and return for a follow-up Visit 9 to end taper. For early terminations, all Visit 8 procedures should be performed and if taper is initiated, subjects should return for follow-up Visit 9.
- h. Cogstate Battery will be completed only for pediatric partial onset seizure subjects (Protocol A0081041) 4-16 years of age.
- i. The follow-up visit is only required for subjects who received taper medication.
- j. All screening procedures must be completed prior to administration of first study medication. All eligibility criteria should be confirmed prior to, or on, Visit 2.
- k. Adjust the dose if needed based on seizure response and tolerability.

\* TC = Telephone Contact to assess dosing and diary compliance, concomitant medications, and AE's.

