**Figure 1. Study Design Schematic**

Subjects who discontinue early and those who complete the study and do not continue treatment with pregabalin are recommended to taper off of study medication (see below for recommended tapering schedule), and will return for Visit 9 when the taper is completed.

For pediatric subjects  $\geq 30$  kg who taper off of pregabalin, the following schedule is recommended:

- Subjects receiving a dose of 10.0 mg/kg/day should receive 5.0 mg/kg/day for 4 days, then 2.5 mg/kg/day for 3 days, then discontinue study medication.
- Subjects receiving a dose of 7.5 mg/kg/day should receive 5.0 mg/kg/day for 4 days, then 2.5 mg/kg/day for 3 days, then discontinue study medication.
- Subjects receiving a dose of 5.0 mg/kg/day should receive 2.5 mg/kg/day for 7 days, and then discontinue study medication.
- Subjects receiving a dose of 2.5 mg/kg/day may discontinue study medication without any taper.

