**Table 1. End-of-Treatment Taper Schedule for Pediatric Subjects >30 kg**

Day  / Total Daily Dose	Day 1	Day 2	Day 3	Day 4	Day 5	Day 6	Day 7/ Follow up
10.0 mg/kg/day	5.0	5.0	5.0	5.0	2.5	2.5	2.5
7.5 mg/kg/day	5.0	5.0	5.0	5.0	2.5	2.5	2.5
5.0 mg/kg/day	2.5	2.5	2.5	2.5	2.5	2.5	2.5
2.5 mg/kg/day	0	0	0	0	0	0	0

1. Days 1-7 post-Month 12/Early Termination visit.

For pediatric subjects <30 kg who taper off of pregabalin, the following schedule is recommended:

- Subjects receiving a dose of 14.0 mg/kg/day should receive 7.0 mg/kg/day for 4 days, then 3.5 mg/kg/day for 3 days, then discontinue study medication.
- Subjects receiving a dose of 10.5 mg/kg/day should receive 7.0 mg/kg/day for 4 days, then 3.5 mg/kg/day for 3 days, then discontinue study medication.
- Subjects receiving a dose of 7.0 mg/kg/day should receive 3.5 mg/kg/day for 7 days, and then discontinue study medication.
- Subjects receiving a dose of 3.5 mg/kg/day may discontinue study medication without any taper.

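### The ±3-day window lets the End of Taper visit (Visit 9) fall on Days 4–6, before the recommended 7-day taper is finished, and CRF recording of non-serious adverse events stops at that visit

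*Protocol*

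**What the plan says.** **Timing of the visit.** Protocol Section 6.16 heads Visit 9 "Follow-up/End of Taper Visit-7 days Post-Completion/Discontinuation±3 Days". The Visit 9 column of the Schedule of Activities gives the same timing, "7 days post completion" with ±3 days. Neither place restricts the early side of the window.

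**Purpose of the visit.** In Section 3.1 (text after Figure 1), subjects who stop pregabalin "are recommended to taper off of study medication" and "will return for Visit 9 when the taper is completed". Schedule footnote g says of subjects who taper after Month 12 that "they will initiate taper at this visit and return for a follow-up Visit 9 to end taper".

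**The taper.** Tables 1–3 in Section 3.1 give a 7-day schedule for every dose level that is tapered. The last column is headed "Day 7/ Follow up", and the footnote defines the days as "Days 1-7 post-Month 12/Early Termination visit". The lowest dose level in each table stops without a taper.

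**Data collection.** Protocol Section 8.2 has adverse events entered on the CRF until the subject's last visit. Separately, serious events are reported to the sponsor until 28 days after the last dose. Section 8.3 includes signs and symptoms of drug withdrawal among possible adverse events. SAP Section 6.2.1 treats events as treatment-emergent until 999 days after the last dose.

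**The concern.** The window and the purpose of the visit disagree. A site that schedules from Section 6.16 or the Schedule is compliant if it sees the subject on Day 4. Section 3.1 and footnote g place the visit at the end of the taper.

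For a tapering subject, Visit 9 is the last scheduled contact. It collects the seizure and dosing diary, and no new diary is issued. After an early visit, the remaining taper days have no scheduled adverse event review, and the final C-SSRS or CBCL has been done before the taper ends. The SAP's long treatment-emergent period does not help, because it classifies events that are recorded and does not extend their collection.

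Whether a new non-serious withdrawal event reaches the adverse event tables would then depend partly on the appointment date. Safety and tolerability is the study's only objective, so that dependence is worth removing.

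**Working it through.** This is day-count arithmetic. No sample size or power formula applies.

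**1. Taper length.** Tables 1–3 contain nine tapered dose levels, three per table.
- Top two levels in each table: 4 + 3 = 7 days.
- Next level: 7 days at one dose.

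All nine therefore give 7 days, which matches the Day 7 heading of the last column.

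**2. Which clock the visit uses.** The table footnotes count taper days from Visit 8 or early termination. Schedule footnote e has early-discontinuing subjects start the taper when discontinuation is decided and adds: "These subjects should return approximately 1 week later for follow-up Visit 9". Both clocks start together, so the visit target cannot mean 7 days after the taper ends.

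**3. Window.** 7 − 3 = Day 4 and 7 + 3 = Day 10, which is 7 in-window days. Days before the last taper day are Days 4, 5 and 6, so 3 of 7.

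**4. What is left after the visit.** Taper days left = max(0, 7 − visit day), with Day 1 the first day after Visit 8. At the top two levels there are three dose reductions. At 10.0 mg/kg/day they are 10.0→5.0 on Day 1, 5.0→2.5 on Day 5, and the stop after Day 7. The 7.5 level has the same three dates, and the <30 kg and adult tables follow the same pattern. At the next level (5.0 mg/kg/day and its equivalents) there are two: Day 1 and the stop.

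| Visit 9 on | Taper days left | Reductions to come, top two levels | Reductions to come, next level |
|---|---|---|---|
| Day 4 | 3 of 7 (43%) | 2 of 3 | 1 of 2 |
| Day 5 | 2 of 7 (29%) | 1 of 3 | 1 of 2 |
| Day 6 | 1 of 7 (14%) | 1 of 3 | 1 of 2 |
| Day 7 | 0 | 1 of 3 | 1 of 2 |
| Days 8–10 | 0 | 0 | 0 |

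**5. Sensitivity to the day numbering.** If the first taper dose is taken on the day of Visit 8, the days left after a Day 4, 5 or 6 visit are 2, 1 and 0. The conflict then remains on Days 4 and 5 only.

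**6. After the change.** A −0/+3 window gives Days 7–10, which is 4 days. None of the 4 falls before the last taper day.

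**The case against.** The strongest reply is that the change does less than it appears to. Counted in dose reductions still to come, moving an early visit to Day 7 helps only Day 4 visits at the top two dose levels, where the count falls from 2 to 1. In every other case a Day 7 visit precedes the stop just as a Day 4–6 visit does. Events caused by stopping are missed at the protocol's own Day 7 target, because drug is still given that day and CRF recording ends at the visit. This is correct. The gain from the edit is 1 to 3 more observed taper days, not observation of the stop.

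Second, other text already points to the end of the taper: Section 3.1, footnote g, the title of Section 6.16 and the table headings. Collection of the dosing diary and the compliance check at Visit 9 also fit a finished taper. That makes early booking less likely, but Section 6.16 and the Schedule set the window and do not forbid it.

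Third, safeguards exist:
- The protocol allows a subject to be seen at any time for safety (Section 6).
- Serious events stay reportable for 28 days after the last dose.
- Events already present at Visit 9 may be followed until they resolve or stabilise (Section 8.1).
- The seizure rate and compliance calculations exclude the taper, and no inference is planned.

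These narrow the gap to a new, non-serious event that starts after an early visit and does not lead to an unscheduled one. They do not close it.

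Finally, the taper is recommended rather than required, so the days left assume that the recommended schedule is followed.

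**Conclusion.** The concern holds. Section 6.16 and the Schedule permit an End of Taper visit on 3 of 7 in-window days that Section 3.1 rules out, with 3, 2 or 1 days of the recommended taper remaining. The counts rest on the table footnotes' day numbering and on the recommended taper being followed. If dosing starts on the day of Visit 8, the conflict covers Days 4 and 5 only.

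The consequence is a possible loss of non-serious adverse events, not a certain one, and it is limited to subjects who taper. How many would be seen early cannot be estimated from the documents. The effect is minor. The correction is still worth making, because the documents give no reason for holding this visit before the taper ends and the edit is cheap.

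**What to change.** In the Visit 9 column of the Schedule of Activities and in Section 6.16, set the visit at *7 days after completion or discontinuation (−0/+3 days), not before the last taper day*, that is Days 7–10. This agrees with Section 3.1 and footnote g. It leaves the Day 7 target, the taper doses and Tables 1–3 unchanged. The cost is one edit in two places and a window of 4 days instead of 7, so sites have less scheduling flexibility.

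If the sponsor also wants the visit to follow the last dose, so that events on stopping can be seen, the window should be Days 8–10. That leaves 3 days and requires the last column heading to change in each of Tables 1–3.
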